4.0 SELECTION AND ENROLLMENT OF **PARTICIPANTS**

- 4.1 Inclusion Criteria
 - 4.1.1 HIV-1 infection, documented by any licensed rapid HIV test or HIV enzyme or chemiluminescence immunoassay (E/CIA) test kit at any time prior to study entry and confirmed by a licensed Western blot or a second antibody test by a method other than the initial rapid HIV and/or E/CIA, or by HIV-1 antigen, or historical plasma HIV-1 RNA viral load.

NOTE: The term "licensed" refers to a US FDA-approved kit, which is required for all IND studies.

WHO (World Health Organization) and CDC (Centers for Disease Control and Prevention) guidelines mandate that confirmation of the initial test result must use a test that is different from the one used for the initial assessment. A reactive initial rapid test should be confirmed by either another type of rapid assay or an E/CIA that is based on a different antigen preparation and/or different test principle (eg, indirect versus competitive), or a Western blot or a plasma HIV-1 RNA viral load.

- 4.1.2 CD4+ T cell count > 350 cells/mm³ ≤ 30 days prior to study entry **at** any US laboratory that has a CLIA (Clinical Laboratory Improvement Amendments) certification or its equivalent.
- 4.1.3 Documentation of virologic suppression defined as:

(a) at least two historical HIV-1 RNA < 50 copies/mL using FDA-approved assay performed by any laboratory that has a CLIA certification or its equivalent while on ART, one of which was obtained between 336 to 31 days, inclusive, prior to study entry and one obtained between 337 and 730 days, inclusive, prior to study entry,

(b) no HIV-1 RNA values \geq 50 copies/mL using a FDA-approved assay performed by any laboratory that has a CLIA certification or its equivalent within 336 days, inclusive, prior to study entry, and

(c) not more than one HIV-1 RNA value equal to or greater than 50 and less than or equal to 200 copies/mL from a result obtained between 337 and 730 days, inclusive, prior to study entry (and no HIV-1 viral load above 200 copies/mL).

4.1.4 Screening plasma HIV-1 quantitative RNA below the limit of detection using an FDA-approved assay with a lower limit of quantification < 50 copies/mL (e.g., < 40 copies/mL obtained by the Abbott Real-Time assay or 20 copies/mL by the Roche Taqman v2.0 assay) performed by any laboratory that has a CLIA certification or its equivalent **obtained** ≤ 30 days prior to study entry.

4.1.5 **Tuberculosis (TB) screening within 365 days of the screening visit diagnosed by tuberculin skin test or interferon gamma release assay.**

4.1.6 Currently on continuous ART for at least 730 days prior to study entry, defined as continuous ART for the 730 days period, inclusive, prior to study entry with no ART interruption longer than 7 consecutive days.

NOTE: The current regimen must include tenofovir/emtricitabine (TDF/FTC) or abacavir/lamivudine (ABC/3TC) + a nonnucleoside reverse transcriptase inhibitor or integrase strand transfer inhibitor (NNRTI or INSTI, not containing cobicistat) for at least 60 days, inclusive, prior to study entry.

- 4.1.7 The following laboratory values obtained \leq 30 days prior to entry by any US laboratory that has a CLIA certification or its equivalent:
 - Absolute neutrophil count (ANC) ≥ **1000**/mm³
 - Hemoglobin ≥ 12.0 g/dL
 - Platelets ≥ 200,000/mm³
 - Calculated creatinine clearance (CrCl) ≥ 80 mL/min (by Cockcroft Gault equation). NOTE: A calculator for estimating the CrCl can be found at www.fstrf.org/ACTG/ccc.html
 - Aspartate aminotransferase (AST) (SGOT) ≤ 1.5x ULN
 - Alanine aminotransferase (ALT) (SGPT) ≤ **1.5**x ULN
 - Alkaline phosphatase ≤ **1.5**x ULN
- 4.1.8 For females of reproductive potential (defined as women who have not been post-menopausal for at least 24 consecutive months, i.e., who have had menses within the preceding 24 months, or women who have not undergone surgical sterilization, specifically hysterectomy and/or bilateral oophorectomy or bilateral salpingectomy) must have a negative serum or urine pregnancy test with a sensitivity of 25 mIU/mL within 72 hours, inclusive, prior to study entry.
- 4.1.9 All **participants** must agree not to participate in a conception process (e.g., active attempt to become pregnant or to impregnate, sperm donation, in vitro fertilization).
- 4.1.10 All **participants** of reproductive potential, who are participating in sexual activity that could lead to pregnancy, must agree to use at least one reliable method of contraception while receiving the study drugs and for 7 weeks after stopping the medications. Acceptable forms of contraceptive include:
 - Condoms (male or female) with or without a spermicidal agent
 - Diaphragm or cervical cap with spermicide

- Intrauterine device (IUD)
- Hormone-based contraceptive (must contain at least 35 mcg of ethinyl estradiol)
- 4.1.11 Women who are not of reproductive potential (women who have been postmenopausal for at least 24 consecutive months or have undergone hysterectomy and/or bilateral oophorectomy or salpingectomy) or men who have documented azoospermia or undergone vasectomy are eligible to start study drugs without requiring the use of contraceptives. Acceptable documentation of sterilization and menopause is specified below.

Written or oral documentation communicated by clinician or clinician's staff of one of the following:

- Physician report/letter
- Operative report or other source documentation in the patient record (a laboratory report of azoospermia is required to document successful vasectomy)
- Discharge summary
- Follicle stimulating hormone-release factor (FSH) measurement elevated into the menopausal range as established by the reporting laboratory.
- 4.1.12 Men and women age \geq 18 and < 75 years.
- 4.1.13 Ability and willingness of **participant** or legal representative to provide written informed consent and attend study visits as scheduled at a participating site.
- 4.2 Exclusion Criteria
 - 4.2.1 A current or past history of progressive multifocal leukoencephalopathy.
 - 4.2.2 Breastfeeding or pregnancy.
 - 4.2.3 Use of strong inhibitors or inducers of CYP3A4 including a protease inhibitor, cobicistat or entry inhibitors as part of the current ART regimen or other concomitant therapy.
 - 4.2.4 Known allergy/sensitivity or any hypersensitivity to components of study drug or their formulation.
 - 4.2.5 Active drug or alcohol use or dependence that, in the opinion of the site investigator, would interfere with adherence to study requirements.
 - 4.2.6 Acute or serious illness or infection requiring systemic treatment and/or hospitalization within 60 days prior to entry.
 - 4.2.7 Vaccinations (other than influenza) \leq 30 days prior to the study entry visit.

NOTE: Influenza vaccine is permitted. **Participants** are encouraged to get this vaccine \geq 7 days prior to the study pre-entry visit.

- 4.2.8 Use of immunomodulators (e.g., interleukins, interferons, cyclosporine), systemic cytotoxic chemotherapy or investigational therapy \leq 60 days prior to study entry.
- 4.2.9 Any current diagnosis or past history of a significant pulmonary, neurologic, cardiac, renal, or hepatic disorder prior to study entry, excluding treated HIV or treated hypertension. Diagnoses that would lead to exclusion include, but are not limited to the following:
 - CDC category C AIDS-indicator conditions NOTE A: Except HIV encephalopathy, HIV wasting, esophageal candidiasis, or pneumocystis pneumonia without dissemination. NOTE B: List available: http://www.cdc.gov/mmwr/preview/mmwrhtml/00018871.htm
 - Varicella zoster
 - Lymphoproliferative malignancy
 - Chronic or severe psychiatric condition
 - Chronic liver disease of any etiology and any degree of severity.
 - Chronic hepatitis
 - Disseminated fungal infection of any type or duration that is not limited to cutaneous or mucocutaneous surfaces
 - A medical disorder that predisposes to bleeding NOTE: If a site investigator is unsure of whether a history of a significant medical or psychiatric condition should lead to participant exclusion, the investigator should err on the side of safety if s/he believes that an active or clinically resolved disorder may put the participant at risk from participation in the study, influence the results of the study, or affect the participant's ability to participate. If still uncertain, then the site should contact the protocol team ([contact]) to assist in a determination.
- 4.2.10 Change in the ART regimen within 12 weeks, inclusive, prior to study entry or intended modification of ART during the study.

NOTE: Modifications of ART doses during the 12 weeks prior to study entry are permitted. In addition, the change in formulation (e.g., from standard formulation to fixed-dose combination) is allowed within 12 weeks prior to study entry. A within class single drug substitution (e.g., switch from nevirapine to efavirenz or from atazanavir to darunavir) is allowed within 12 weeks prior to study entry, with the exception of a switch between any other NRTI to/from abacavir. No other changes in ART within the 12 weeks prior to study entry are permitted. However, participants need to be receiving (and tolerating) an allowable (for study purposes) ART regimen for at least 4 weeks prior to study entry.

4.2.11 History of untreated latent tuberculosis infection (LTBI) diagnosed by tuberculin skin test or interferon gamma release assay. LTBI treatment would consist of 9 months of isoniazid or an equivalent therapy **completed at least 4 weeks prior to study entry**.

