The safety profile of ruxolitinib in individuals with myelofibrosis has been welldocumented and FDA-approved for this indication. Emerging data have shown that even fewer AEs have been reported in individuals without myelofibrosis (solid tumors and RA). We believe that the population of individuals living with HIV-1 who would be eligible for this study is immunologically and hematologically "healthier" than individuals with myelofibrosis and therefore should have few AEs.

Justification for the Participant Population Selected

Virologically Suppressed on ART

In order to assess the impact of ruxolitinib on chronic inflammation and systemic immune activation, it was important to exclude the impact of ART on these same markers through mechanisms dependent on and independent of viral replication.

Age and CD4+ T Cell Criteria

In order to minimize AEs associated with ruxolitinib, we chose a **participant** population with an adequate CD4+ T cell -count and within a safe age range, \geq 18 to < 75. Furthermore, the immune system of adults and children of ages outside of this range behave differently, which could introduce additional confounders into the efficacy assessment.

Exclusion of Pregnant Women

Ruxolitinib has been designated pregnancy category C. In animal studies, treatment with ruxolitinib resulted in an increase in late resorptions and reduced fetal weights at maternally toxic doses. There are no adequate and well-controlled studies of ruxolitinib in pregnant women.

Exclusion of **Participants** with Hepatitis B Virus (HBV) or Hepatitis C Virus (HCV) Infection

According to Incyte Corporation, there are only five **participants** with HBV infection and no **participants** with HCV infection who received ruxolitinib. Additionally, two case reports of HBV reactivation in individuals receiving ruxolitinib for myelofibrosis were published [61, 62]. Therefore, it was recommended that **participants** with HBV infection or HCV infection be excluded from this study.

Risk Benefit Assessment

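### The rationale excludes HBV and HCV infection, but the criteria act only on a known diagnosis and no hepatitis result is required before randomisation

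*Protocol*

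**What the plan says.** **Intent.** Protocol 2.2 has a paragraph on this exclusion, which recommends that participants "with HBV infection or HCV infection be excluded from this study". Two grounds are given. The first is sparse exposure: "According to Incyte Corporation, there are only five" participants with HBV who had received the drug, and none with HCV. The second is that "two case reports of HBV reactivation in individuals receiving ruxolitinib for myelofibrosis were published".

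**Operative rule.** Section 4.2.9 excludes "Any current diagnosis or past history of a significant pulmonary, neurologic, cardiac, renal, or hepatic disorder prior to study entry", followed by a list that is expressly not exhaustive. The list includes "Chronic liver disease of any etiology and any degree of severity" and "Chronic hepatitis". Neither HBV nor HCV is named anywhere in 4.2.

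**Laboratory requirements.** The liver-related entry limits in 4.1.7 are "Aspartate aminotransferase (AST) (SGOT) ≤ 1.5x ULN" and the same multiple for ALT and alkaline phosphatase. The liver panel in 6.3.9 consists of these three enzymes plus bilirubin fractions. Section 6.1 has no hepatitis row at any visit. Section 6.3.2 records chronic or acute HBV and HCV as medical history.

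**Tuberculosis.** Section 4.1.5 requires "Tuberculosis (TB) screening within 365 days of the screening visit diagnosed by tuberculin skin test or interferon gamma release assay", and 4.2.11 separately excludes a history of untreated latent infection.

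**The concern.** The rationale speaks of infection, while the criterion speaks of a diagnosed condition. The two agree only for people whose status is already known. For the rest, nothing in the eligibility or screening sections would reveal the infection, because liver enzymes below a ceiling do not establish whether either virus is present.

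Two things are at stake. First, a person whom the protocol meant to keep off ruxolitinib could receive it: for HBV, in the face of a reported reactivation risk; for HCV, with no prior exposure data at all. Second, 7.2.8 asks the site to rule out viral hepatitis when AST or ALT reaches Grade 3 and to judge whether the rise is related to the drug. Without a baseline result, the site may be unable to tell a pre-existing infection from a new one.

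**Working it through.** The plan states no figure on this point, so the check sets the sections side by side.

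| Step | Section | What it requires | Detects undiagnosed HBV or HCV? |
|---|---|---|---|
| Rationale | 2.2 | Exclude infection with either virus | States the aim only |
| Exclusion | 4.2.9 | Diagnosis or history, including chronic liver disease or chronic hepatitis | No |
| Inclusion laboratory limits | 4.1.7 | AST, ALT, alkaline phosphatase each at most 1.5 times the upper limit | No; enzymes only |
| Medical history | 6.3.2 | Record HBV or HCV whenever diagnosed | No |
| Schedule of Events | 6.1 | Liver function tests, no hepatitis row | No |
| Laboratory list | 6.3.9 | Enzymes and bilirubin | No |
| Toxicity management | 7.2.8 | Rule out viral hepatitis at Grade 3 AST/ALT | Only after the event |

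No step before randomisation establishes infection status in a person without a diagnosis.

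**Comparison with tuberculosis.** The safety discussion in 2.2 lists reactivated latent tuberculosis and hepatitis B in one sentence as reported on ruxolitinib. Tuberculosis has both a history exclusion (4.2.11) and a test within 365 days (4.1.5). Hepatitis has the history exclusion alone.

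**Which safety results depend on relatedness.** Protocol 9.6.1 and SAP 2.4.1 define two composites.
- Single-arm ruxolitinib proportion (SAP primary outcome 1): counts Grade 4 or recurrent Grade 3 toxicity only if related to study drug. A relatedness judgement can change it.
- Between-arm comparison (SAP primary outcome 2): counts such toxicity whatever the cause. A relatedness judgement cannot change it.

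**Illustration of size, under assumption only.** Let p be the share of otherwise eligible candidates with undiagnosed HBV or HCV; the documents do not give it. The ruxolitinib arm has 40 participants (9.4.2). Expected number = 40p; chance of at least one = 1 − (1 − p)^40.

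| Assumed p | Expected of 40 | Chance of at least one |
|---|---|---|
| 0.5% | 0.2 | 18% |
| 1% | 0.4 | 33% |
| 2% | 0.8 | 55% |
| 5% | 2.0 | 87% |

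These are counts of carriers, not of reactivations or harms.

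**The case against.** Several points on the other side are sound.

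- **Known infection is already covered.** Section 4.2.9 is broad and its list is open-ended. Investigators in doubt about a past or resolved condition are told to favour caution, and 6.3.2 asks for HBV and HCV whenever diagnosed. A reader might infer that the exclusion is not enforced at all, but the documents do not support that. The gap is confined to undiagnosed infection with enzymes inside the limits. The instruction on caution does not close it, since it concerns a history the site knows about.
- **Tuberculosis is the exception.** A reader might infer that hepatitis alone is handled more loosely. Section 2.2 also lists PML, herpesvirus infection, *Pneumocystis*, toxoplasmosis and cryptococcal disease, and no entry test is required for these either. What remains of the comparison is narrower: the rationale gives HBV and HCV an exclusion of their own, and the protocol shows with tuberculosis that it can pair such an exclusion with a test.
- **Reactivation is not the whole rationale.** It is reported for HBV only. The HCV exclusion rests on absent exposure data.
- **Monitoring is frequent.** Liver tests are scheduled at weeks 1, 2, 4, 5, 10 and 12, and 7.2.8 requires the drug to be discontinued or held at Grade 3 or above. This limits harm once it appears but does not prevent enrolment.
- **The formal safety test is not distorted by attribution.** A reader might infer that it is, but the between-arm composite disregards relatedness.
- **Some sources are unseen.** Consent pages, the laboratory processing chart and the screening checklist are not available. SAP 2.1 also lists eligibility terms that differ from this protocol version (a 45-day CD4 window, TAF/FTC), so later changes may exist. Nothing shows that hepatitis testing was among them, and a test mentioned only in those papers would not be an eligibility requirement in sections 4 or 6.

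**Conclusion.** The concern holds in a bounded form. Protocol 2.2 states a safety exclusion for HBV and HCV infection. Sections 4.2.9, 4.1, 6.1 and 6.3.9 deliver it only for chronic infection that is already diagnosed. A person with undiagnosed infection and AST, ALT and alkaline phosphatase at or below 1.5 times the upper limit could be randomised and treated, with no required baseline result for the assessment that 7.2.8 asks for.

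Within the safety composites, the consequence of uncertain attribution is limited to the single-arm ruxolitinib proportion. No sample size, power or error rate is affected. The number of people involved is unknown: the table shows how it depends on an assumed prevalence, and the finding does not rest on any row of it. It rests on the text of the protocol version supplied, so confidence is moderate. The change is worth making because a stated safety exclusion is not fully carried out by the operative rules and the remedy is inexpensive.

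**What to change.** Reconcile 2.2 with 4.2.9 and 6.1:

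1. Name HBV and HCV infection in 4.2, so that the criterion has the same scope as the rationale.
2. Require a documented result that establishes infection status before randomisation. Accept a chart result within a stated window; otherwise test on the screening blood draw. The markers and the window are for the sponsor to choose.
3. Add the matching row to 6.1 and the entry to 6.3.9. The result would then also serve as the baseline for 7.2.8.

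The cost is a few lines of protocol text, routine assays on blood already drawn for candidates without a recent result, and a small number of additional screen failures.

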4.3.2 Randomization/Participant Registration

Participants who meet enrollment criteria will be registered to the study according to standard ACTG DMC procedures. For **participants** from whom informed consent has been obtained, but who are deemed ineligible or who do not enroll into the initial protocol step, an ACTG Screening Failure Results form must be completed and keyed into the database.

4.4 Coenrollment Guidelines

- Sites are encouraged to coenroll participants in A5128, "Plan for Obtaining Informed Consent to Use Stored Human Biological Materials (HBM) for Currently Unspecified Analyses," and A5351s, "Effect of Immune-Modulatory Interventions on Cytomegalovirus Replication during Suppressive Antiretroviral Therapy"
- Coenrollment in A5128 and A5351s does not require permission from the A5336 protocol chairs.
- For specific questions and approval for coenrollment in other studies, sites should contact the protocol team via e-mail as described in the Study Management section.

5.0 STUDY TREATMENT

5.1 Regimens, Administration, and Duration

Study treatment is defined as ruxolitinib. **Participants** will be randomized at a 2:1 ratio to either 5 weeks of treatment with ruxolitinib or no study treatment as follows:

ARM A: Ruxolitinib 10 mg PO BID with or without food. **Participants must remain on ART regimen (not provided by the study) for the duration of the study.**

ARM B: No study treatment. **Participants should be encouraged to remain on ART regimen for the duration of the study.**

Participants in Arm A should be instructed not to drink grapefruit juice **or eat grapefruit** while taking ruxolitinib. **Participants** will remain on study treatment for five weeks and **be** followed for seven weeks after treatment discontinuation. **Participants** will be on study for **a total of** 12 weeks.

5.2 Study Product Formulation and Preparation

Ruxolitinib tablets 10mg should be stored at room temperature between 20° and 25°C (68° and 77°F). Excursions permitted between 15°C and 30°C (59°F and 86°F). See USP controlled room temperature.

- 5.3 Pharmacy: Product Supply, Distribution, and Accountability
 - 5.3.1 Study Product Acquisition/Distribution

Ruxolitinib, manufactured by Incyte Corporation, will be provided by Emory University and available through the NIAID Clinical Research Products Management Center (CRPMC). The site pharmacist should obtain the study product(s) for this protocol by following the instructions in the manual Pharmacy Guidelines and Instructions for DAIDS Clinical Trials Networks. 5.3.2 Study Product Accountability

The site pharmacist is required to maintain complete records of all study products received from the NIAID CRPMC and subsequently dispensed. All unused study products in CRSs must be returned to the NIAID CRPMC (or as otherwise directed by the sponsor) after the study is completed or terminated. The procedures to be followed are in the manual Pharmacy Guidelines and Instructions for DAIDS Clinical Trials Networks.

5.4 Concomitant Medications

Whenever a concomitant medication or study agent is initiated or a dose changed, investigators must review the concomitant medication's and study agent's most recent package insert, Investigator's Brochure, or updated information from DAIDS to obtain the most current information on drug interactions, contraindications, and precautions.

Additional drug information may be found on the updated ACTG Drug Interactions Database located at: http://tprc.pharm.buffalo.edu/home/di_search/

5.4.1 Prohibited Medications

A list of prohibited medications can be found on the protocol-specific web page (PSWP), https://member.actgnetwork.org/study/53292#profile=4.

5.4.2 Precautionary Medications

A list of precautionary medications is posted on the PSWP, https://member.actgnetwork.org/study/53292#profile=4.

6.0 CLINICAL AND LABORATORY EVALUATIONS

6.1 Schedule of Events

Evaluation	Screening Pro	Pre-Entry	Entry		(On-Study (W	Evaluati eeks)				
				1	2	4	5	10	12	Confirmation	Premature
Window	≤30 days before entry	≥24 hours after screening and ≤7 days before entry		± 3 days			± 7 days		of Virologic Failure	Treatment/Study Discontinuation Evals.	
Documentation of HIV-1	Х										
Medical History	Х		Х								
Medication History	Х		Х								
Complete Physical Examination		х									
Targeted Physical Examination	x		Х	х	Х	Х	х	х	х		Х
Clinical Assessments			Х	Х	Х	Х	Х	Х	Х		Х
Concomitant Medications	Х		Х	Х	Х	Х	Х	Х	Х		Х
Study Treatment Modifications	х		Х	х	Х	Х	х	Х	х		Х
ART Modifications	Х		Х	Х	Х	Х	Х	Х	Х		Х
Hematology	Х		Х	Х	Х	Х	Х	Х	Х		Х
Liver Function Tests	Х		Х	Х	Х	Х	Х	Х	Х		Х
Blood Chemistries	Х		Х	Х	Х	Х	Х	Х	Х		Х
Fasting Lipid Panel			Х				х				X (if prior to week 5)
Pregnancy Testing	Х		X1			If sus	spected				
Nadir CD4+ T cell Count			Х								
Documentation of Pre- ART CD4+ T cell Count			Х								
CD4+/CD8+	Х	X ²	Х		Х		Х		Х		Х

Evaluation	Screening Pre	Pre-Entry	Entry		(Dn-Study (Wo	Evaluati eeks)				
				1	2	4	5	10	12	Confirmation	Premature
Window	≤30 days before entry	≥24 hours after screening and ≤7 days before entry		± 3 days			± 7 days		of Virologic Failure	Treatment/Study Discontinuation Evals.	
Stored PBMCs for Other Immunologic Studies			Х				х		х		х
Stored Plasma Soluble Markers		Х	Х			Х	х		х		Х
Stored Plasma Soluble Marker:IL-6		Х	Х			Х	х	х	х		×
Documentation of Pre- ART HIV-1 RNA			Х								
Plasma HIV-1 RNA	Х		Х		Х		Х		Х	Х	Х
Stored Plasma HIV-1 RNA for Single Copy Assay			Х				х		х		Х
Stored PBMC Reservoir Assays			Х				х		х		Х
Stored Plasma/PBMC		Х	Х		Х		Х		Х		Х
Stored Oral Swabs for HHV		x	X	х	X	x	х	x	x		X
Plasma PK Collection for Arm A				х		х					X (if prior to week 4)
Medication Diary for Arm A (D=Distribute; C=Collect)			X (D)	X (C)	X (D)	X (C)					X (C) (if prior to week 4)
Adherence Assessment			Х	Х	Х	Х	Х	Х	Х		Х

¹Refer to section 6.2.2 for pregnancy testing at study entry. ²Only one CD4+/CD8+ is required if screening and pre-entry visits are combined.

